15.5 Date of most current exacerbation:   unknown						
MMM	YYYY					

Evidera 138 Site Page 7 of 7

Evidera # 138 Plate # 007 Visit # 001

Participant ID

██████████

16. Following the use of the PRECISION program, which of the following will you do to the patient's medication after today's telehealth visit? (check all that apply)

- Step-down of controller medicines
- No change to the level of controller therapy
- Step-up of controller medicines
- Prescribe a course of systemic corticosteroids
- Begin work-up for possible biologic
- Begin biologic: (specify): _____
- Other: (specify): _____

Part 4. Asthma Checklist (Assess content only)

1. Please check the Asthma Checklist Assess items (page 1) that were considered during the visit:

CONSIDER FOR ALL PATIENTS REGARDLESS OF ASTHMA CONTROL		CONSIDER FOR PATIENTS WITH UNCONTROLLED SYMPTOMS AND/OR RISK FACTORS FOR EXACERBATIONS	
 Adherence ^{1,3}	 Appropriate Therapy ^{1,3}	 Asthma Phenotyping ^{1,4}	 Referral to an Asthma Specialty Center, or Other Appropriate Specialist or Health Care Provider in Your Area ^{1,2}
 Asthma Action Plan ^{1,2,4}	 Comorbidities ^{1,2}	 Home and/or Work Exposures ^{1,2,4}	 Alternative Diagnoses and Hidden Comorbidities ^{1,2}
 Inhaler Technique ^{1,2,4}			 Optimizing Therapy with Add-on or Advanced Treatment ^{1,3}
 Psychological Issues ^{1,2}			
 Spirometry ^{1,2,4}			
 Tobacco Use ^{1,2,5}			
 Vaccinations ^{1,2,6,7}			

Investigator/Coordinator Signature: _____

Date:

DD	MMM	2	0	

 YYYY

APPENDIX J. FOLLOW-UP CRFS

Follow-up Clinical Case Report Form

Evidera 138												Site	Page 1 of 5				
Evidera # 138						Plate # 009						Visit # 003					
Participant ID						Date of Visit											
_____			_____			_____			20			_____			_____		
DD	MMM	YYYY															

Follow-up Clinical Case Report Form

Part 1. CLINICAL INFORMATION

1. Platform used for follow-up appointment : telehealth in-person office visit
2. During the visit, how was the AIRQ™ administered?
 Interviewer Patient self-completed
3. During the visit, was the patient able to see their risk score on the ruler included in the AIRQ™?
 Yes No

If yes, how were patients able to view their risk score?

- On their phone
- On their computer
- Paper copy of AIRQ™ mailed to patient before the visit or provided at in-person visit
- Other, please specify: _____

4. Reason for visit:
 Scheduled follow-up
 Exacerbation
 Other _____

If exacerbation: date of exacerbation start:

DD	MMM	YYYY					

5. How would you rate this patient's asthma severity?
 Intermittent
 Mild persistent
 Moderate persistent
 Severe persistent
6. Did the patient previously have COVID or do they currently have COVID?
 Yes No Unknown

[figure not shown]
[figure not shown]
Evidera 138	Site	Page 2 of 5
		
Evidera # 138	Plate # 010	Visit # 003
Participant ID 		

7. Please indicate all current medications and any changes that have occurred since the last study visit:

MAINTENANCE PHARMACOLOGIC THERAPY Please check all that apply .	
Please check all current medications the patient is taking	
 ICS only  Low dose  Medium dose  High dose  ICS/LABA  Low dose  Medium dose  High dose  LABA (Single inhaled medicine, not in a fixed-dose combination with an ICS or ICS/LAMA)  LAMA (single inhaled medicine used with or without other inhaled therapies or alone)  ICS/LABA/LAMA (fixed-dose combination)  Leukotriene modifier  Theophylline Preparations  Macrolides Add-on Therapy Biologics  Cinqair (reslizumab)  Dupixent (dupilumab)  Fasenra (benralizumab)  Nucala (mepolizumab)  Xolair (omalizumab)  Other: _____	Rescue Therapy  SABA alone with no maintenance therapy  SABA with maintenance therapy  Primatene Mist as a rescue and no maintenance therapy  Primatene Mist as a rescue with maintenance therapy(s)  ICS+SABA as rescue therapy alone  ICS+SABA as rescue therapy with maintenance therapy(s)  Fixed dose combination fast-acting LABA/ICS alone as rescue  Fixed dose combination fast-acting LABA/ICS as rescue and maintenance therapy  SABA as rescue therapy via nebulizer with other rescue or maintenance therapies  SABA as rescue therapy via nebulizer without other rescue or maintenance therapies
Chronic Oral Corticoid Steroid Therapy  Prednisone _____ mg  QD  QOD  Other (specify): _____	
Note: please see Appendix DD for a description of drugs in each class listed above	

Evidera 138	Site	Page 3 of 5
		
Evidera # 138	Plate # 011	Visit # 003
Participant ID 		

8. Please indicate asthma exacerbation history since last visit:

ASTHMA EXACERBATION HISTORY		 Not applicable
An asthma exacerbation is defined by a change in asthma control requiring a course of oral steroids (i.e., at least 3 days with at least 10 days between each burst) and/or steroid injection and/or a hospitalization for asthma or emergency department visit for an asthma exacerbation. Importantly, record only the highest utilization for each exacerbation, do not double count exacerbation episodes. If an OCS course was due to a hospitalization, do not record as OCS course but as the hospitalization		
8.1	Number of times since the last visit that asthma symptoms required an emergency department or urgent care visit (but not an overnight stay in the hospital):	 ER/urgent care visits (with no overnight hospital stay)  None
8.2	Number of times since the last visit that there was a worsening in asthma symptoms that required a hospital stay for greater than 24 hours:	 times admitted to hospital  None
8.3	Number of unplanned ambulatory clinic visits due to exacerbation since the last visit:  unplanned visit—Please list dates of the most recent unplanned ambulatory clinic visit below (DD-MMM-YYYY)	 None
a.	 	  None
b.	 	
c.	 	
d.	 	
e.	 	
8.4	How many courses of oral corticosteroids (OCS) was the patient prescribed since the last study visit for asthma exacerbations unrelated to emergency department, urgent care or, unplanned ambulatory clinic visits or hospitalizations?	 0 OCS courses for asthma  1 OCS course only for asthma  2 OCS courses only for asthma  3 OCS courses for asthma  ≥ 4 OCS courses for asthma  patient is on daily OCS
8.5	Date of most current exacerbation:	   unknown

Evidera 138	Site	Page 4 of 5
		
Evidera # 138	Plate # 012	Visit # 003
Participant ID		

9. What is your assessment of the patient's overall asthma control?

- Completely controlled
- Well controlled
- Somewhat controlled
- Poorly controlled
- Not controlled

Part 2. Asthma Checklist (Assess content only)

1. Please check the Asthma Checklist Assess items (page 1) that were considered during the visit:

CONSIDER FOR ALL PATIENTS REGARDLESS OF ASTHMA CONTROL		
 Adherence ¹⁻³	 Appropriate Therapy ^{1,2}	 Referral to an Asthma Specialty Center, or Other Appropriate Specialist or Health Care Provider in Your Area ^{1,2}
 Asthma Action Plan ^{1,2,4}	 Comorbidities ^{1,2}	 Alternative Diagnoses and Hidden Comorbidities ^{1,2}
 Inhaler Technique ^{1,2,4}	 Home and/or Work Exposures ^{1,2,4}	 Optimizing Therapy with Add-on or Advanced Treatment ^{1,3}
 Psychological Issues ^{1,2}		
 Spirometry ^{1,2,4}		
 Tobacco Use ^{1,2,5}		
 Vaccinations ^{1,2,6,7}		

2. Following the use of the PRECISION program, which of the following will you do to the patient's medication after today's visit? (check all that apply)

- Step-down of controller medicines
- No change to the level of controller therapy
- Step-up of controller medicines
- Prescribe a course of systemic corticosteroids
- Begin work-up for possible biologic
- Begin biologic: (specify): _____
- Other: (specify): _____

[figure not shown]
Observational Study Protocol
Study Code D2287L00028 [EVA-26645-03]
Version 2.0
Date June 16, 2022

Evidera 138	Site	Page 5 of 5
		
Evidera # 138	Plate # 013	Visit # 003
Participant ID		
		

For AAN and Third Party Payer Sites ONLY

1. Date of last coaching/follow-up session:   
DD MMM YYYY
2. Number of coaching/follow-up sessions: 

Investigator/Coordinator Signature: _____

Date:   
DD MMM YYYY

12-Month Post-Initial Visit Exacerbation Clinical Case Report Form

Participant ID: ____ - ____

Verbal Consent Provided: Yes No

Date verbal consent provided: MM/DD/YYYY

Date form completed: MM/DD/YYYY

Please indicate the asthma exacerbation history since the patients initial study visit (12 months ago):

ASTHMA EXACERBATION HISTORY		 Not applicable
An asthma exacerbation is defined by a change in asthma control requiring a course of oral steroids (i.e., at least 3 days with at least 10 days between each burst) and/or steroid injection and/or a hospitalization for asthma or emergency department visit for an asthma exacerbation. Importantly, record only the highest utilization for each exacerbation, do not double count exacerbation episodes. If an OCS course was due to a hospitalization, do not record as OCS course but as the hospitalization		
8.1	Number of times since the last visit that asthma symptoms required an emergency department or urgent care visit (but not an overnight stay in the hospital):	
	 ER/urgent care visits (with no overnight hospital stay)	 None
8.2	Number of times since the last visit that there was a worsening in asthma symptoms that required a hospital stay for greater than 24 hours:	
	 times admitted to hospital	 None
8.3	Number of unplanned ambulatory clinic visits due to exacerbation since the last visit:	
	 unplanned visit—Please list dates of the most recent unplanned ambulatory clinic visit below (DD-MMM-YYYY)	
a.		 None
b.		
c.		
d.		
e.		
8.4	How many courses of oral corticosteroids (OCS) was the patient prescribed since the last study visit for asthma exacerbations unrelated to emergency department, urgent care or, unplanned ambulatory clinic visits or hospitalizations?	
	 0 OCS courses for asthma  1 OCS course only for asthma  2 OCS courses only for asthma  3 OCS courses for asthma  ≥ 4 OCS courses for asthma  patient is on daily OCS	
8.5	Date of most current exacerbation:	   MMM     YYYY  unknown

Investigator/Coordinator Signature: _____

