Appendix J).

4.1.5 12-Month Post-Initial Visit Exacerbation Clinical Case Report Form (CRF)

For each consented participant from the sites selected for the pre/post exacerbation data comparison, the site will complete a follow-up clinical case report form that includes chart-reported exacerbations 12-months after the initial study visit (Appendix J).

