6. STUDY CONDUCT AND REGULATORY DETAILS

6.1 Study Conduct

6.1.1 Study Flow Chart and Plan for Telehealth or In-Person Visits

Figure 1. Study Flow Overview of Initial Telehealth or In-Person Visit

[figure not shown]

Figure 2. Overview of the Follow-up Telehealth or In-person Visit Study Flow

[figure not shown]

Table 1. Study Plan

Study Procedure	Timing	Completed by:	
		Clinical Site (Staff/HCP)	Patient
Telephone Introduction to Study	At time of appointment reminder (if not automated)	X	
Introduction to Study	At the initial visit (telehealth; in-person)	X	
Document Consent/Accent	At the initial visit (telehealth; in-person)	X	
Clinical CRF, which includes the Assess component of the Asthma Checklist (page 1)	At the initial visit (telehealth; in-person)	X	
AIRQ™	At the initial visit (telehealth; in-person)		X
ACE Questionnaire	Sent to patient within approx. 48 hours following initial visit via e-mail link (two email reminders)		X
CCI	[REDACTED]		X
CCI	[REDACTED]		X

Study Procedure	Timing	Completed by:	
		Clinical Site (Staff/HCP)	Patient
Patient Sociodemographics Questionnaire	Sent to patient within approx. 48 hours following initial visit via e-mail link (two email reminders)		X
AIRQ™ 3-month Recall	Used at the follow-up visit (telehealth; in-person), should a follow-up visit occur		X
Follow up Clinical CRF, which includes the Assess component of the Asthma Checklist(page 1)	Used at the follow-up visit (telehealth; in-person), should a follow-up visit occur	X	
Clinical Site Touchpoint Questions	Up to 4 meetings over the 6-month patient recruitment period	X	
Post-study Survey	After patient enrollment is nearly completed (approximately 30 telehealth visits)	X	
Qualitative Interviews with Site Principal Investigator and Key Staff	After patient enrollment is completed	X	
12 Month Post-Initial Visit Exacerbation CRF	Used to collect 12-month post-initial visit exacerbation data for patients at selected sites who consented	X	

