The study team originally planned to collect exacerbation data to compare 12 months pre-initial visit to 12 months post-initial visit among patients from third-party payer sites. However, these sites were unable to participate in the study. Therefore, high performing sites were selected to recontact their participants to ask if they would be willing to participate in a chart review to be conducted 12 months after their initial study visit. If patients agree, sites will use a new verbal consent script specific for the 12-month post-initial visit exacerbation data. For patients who consent, the site will complete a 12-month post-initial visit exacerbation CRF form. Data will only be collected for patients who provide their verbal consent. Verbal consent will be documented on the 12-month post-initial visit exacerbation CRF form. This will be compared to the exacerbation data 12 months pre-initial visit, which was collected as part of the planned clinician-completed CRF form. Evidera will host a 30-minute conference call with each clinical site for up to four (4) time points (touchpoints) at Months 1, 2, 3 (optional), and 6 to discuss the use of the PRECISION tools, address site questions, and discuss a set of touchpoint questions that focus on the challenges and facilitators of implementing the PRECISION program. These meetings will also be used to identify any sites that may benefit from participating in a re-training session (budget assumes up to six sites will need re-training). The optional month three (3) touchpoint will be based on whether the site is having any difficulties with the study.

After patient enrollment has been completed, prescribing providers at clinical sites, nurse case managers, or the asthma coaches from the telehealth component of Asthma and Allergy Network who treated at least 10 patients will complete the Post-study Survey. Evidera will provide the participating HCP with Post-study Survey, via an email PDF attachment (to be self-completed by the HCP). The emailed survey will have a pre-populated header with a unique participant ID number.

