15.1 Number of times in the past 12 months asthma symptoms required an emergency department or urgent care visit (but not an overnight stay in the hospital):						
	ER/urgent care visits (with no overnight hospital stay)	 None				
15.2 Number of times in the past 12 months that there was a worsening in asthma symptoms that required a hospital stay for greater than 24 hours:						
	times admitted to hospital	 None				
15.3 Number of unplanned ambulatory clinic visits due to exacerbation in past 12 months :						
	unplanned visit—Please list dates of the most recent unplanned ambulatory clinic visit below (DD-MMM-YYYY)					
a.						 None
b.						
c.						
d.						
e.						
f.						
15.4 How many courses of oral corticosteroids (OCS) was the patient prescribed over the past 12 months for asthma exacerbations unrelated to emergency department, urgent care or, unplanned ambulatory clinic visits or hospitalizations?						
 0 OCS courses for asthma within 12 months						
 1 OCS course only for asthma within the past 12 months						
 2 OCS courses only for asthma within the past 12 months						
 3 OCS courses for asthma within the past 12 months						
 ≥ 4 OCS courses for asthma within the past 12 months						
 patient is on daily OCS						

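### The 12-month exacerbation form names two different counting windows, and a literal answer to its items would shorten only the post-visit period in patients who had a follow-up study visit

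*Protocol*

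**What the plan says.** **The intended window is 12 months from the initial visit.** The lead-in of the 12-month form in Protocol Appendix J reads "Please indicate the asthma exacerbation history since the patients initial study visit (12 months ago". Protocol section 4.1.5 describes the form as holding "chart-reported exacerbations 12-months after the initial study visit". Table 1 in section 6.1.1 lists it as "Used to collect 12-month post-initial visit exacerbation data for patients at selected sites who consented". Section 6.1.2 gives the use: "This will be compared to the exacerbation data 12 months pre-initial visit".

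**The items on the same form say something else.** Item 8.1 asks for the "Number of times since the last visit that asthma symptoms required an emergency department or urgent care visit". Items 8.2 (hospital stays) and 8.3 (unplanned ambulatory visits) take the same start point. Item 8.4 asks how many oral corticosteroid (OCS) courses "was the patient prescribed since the last study visit for asthma exacerbations". Item 8.5, the date of the latest exacerbation, states no window.

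**The item wording matches the Follow-up Clinical CRF.** That form, also in Appendix J, has the same item numbers. There the wording fits, because its own lead-in is "Please indicate asthma exacerbation history since last visit".

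**The pre-visit form has a fixed window.** Item 15 of the Clinical CRF (Appendix I) covers the prior 12 months throughout; item 15.2, for example, asks for the "Number of times in the past 12 months that there was a worsening in asthma symptoms that required a hospital stay".

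**The concern.** Each count is written beside an item that names one window, under a lead-in that names another, and no visible passage says which prevails. Follow-up study visits can fall between the initial visit and month 12, so the two windows can differ. SAP section 3 defines a follow-up analysis set with visits in the nine-month implementation period, and SAP Appendix B records only one follow-up visit per patient.

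The post count is set against the same patient's own 12-month pre count, with no control group. A literal answer shortens the post side and leaves the pre side untouched, so it would look like fewer exacerbations after the program even if nothing had changed.

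**Working it through.** **Step 1: when do the windows differ?**

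| Patient | Lead-in | Items 8.1–8.3, read literally | Item 8.4, read literally |
|---|---|---|---|
| No follow-up study visit | 12 months | 12 months, if *last visit* means a study visit | 12 months |
| Follow-up study visit at month f | 12 months | 12 − f months | 12 − f months |

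The conflict therefore affects counts in patients who had a follow-up study visit.

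**Step 2: one patient.** Assume a constant event rate and a literal answer. The captured share is (12 − f)/12, so the spurious fall is f/12. SAP section 5.1.2 groups elapsed time to follow-up as 0–3, 4–6 and 7–9 months. The band limits give:

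- f = 3: 3/12 = 25%
- f = 4: 4/12 = 33%; f = 6: 6/12 = 50%
- f = 7: 7/12 = 58%; f = 9: 9/12 = 75%

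The last band fits the nine-month implementation stage but not the 6-month follow-up period in Protocol section 6.1.2.

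**Step 3: the sample.** Let s be the share of expected events in patients whose forms were answered literally, with a common f. The overall fall is s × f/12. The documents give no value for s, so these are assumptions:

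| s | f = 3 | f = 6 | f = 9 |
|---|---|---|---|
| 0 (sites followed the lead-in) | 0% | 0% | 0% |
| 0.25 | 6% | 12.5% | 19% |
| 0.5 | 12.5% | 25% | 37.5% |

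**Step 4: categorical OCS use (illustration only).** SAP Appendix B reports a Bowker's test of within-patient change in OCS use (Table 31b) but does not say which form or item supplied it. Suppose it were item 8.4, with categories 0, 1, 2, 3 and ≥4, leaving out the item's separate daily-OCS option. Take pre ~ Poisson(1) and post ~ Poisson((12 − f)/12), independent, with no true change.

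- Full window: P(down) = P(up) = 0.346, ratio 1.
- Every form shortened, f = 3: 0.404/0.266 = 1.52.
- Every form shortened, f = 6: 0.470/0.181 = 2.60.

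Now let s be the share of analysed patients with a shortened window, and mix the probabilities:

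- s = 0.25, f = 3: (0.75 × 0.346 + 0.25 × 0.404)/(0.75 × 0.346 + 0.25 × 0.266) = 1.11; f = 6: 1.24.
- s = 0.5, f = 3: (0.346 + 0.404)/(0.346 + 0.266) = 1.23; f = 6: (0.346 + 0.470)/(0.346 + 0.181) = 1.55.

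**Step 5: would the data reveal it?** Two checks were sized for a window that began at the follow-up visit, at assumed rates of λ = 0.5 to 2 events a year in a category.

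- *Counts.* A 12-month count below the Follow-up CRF count in the same category reveals a shortened window. With the Follow-up CRF count ~ Poisson(λf/12) and the 12-month count ~ Poisson(λ(12 − f)/12), this flags 8–12% of shortened windows at f = 3 and 18–35% at f = 6.
- *Dates.* Item 8.3 has lines for full dates on both forms. An unplanned visit dated on the Follow-up CRF but missing from the 12-month form points to a shortened window. With complete lists, the chance of at least one such date is 1 − exp(−λf/12): 12–39% at f = 3 and 22–63% at f = 6, for that item only.

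Item 8.5 can also help. A latest exacerbation dated between the initial and follow-up visits, beside counts of zero, suggests the shorter window; beside a positive count it suggests the longer one.

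**The case against.** The strongest reply is that the intended window is not in doubt. The title, the lead-in and the protocol body all agree on it, and the form is completed only after a separate consent to a chart review 12 months after the initial visit. A site could easily read the items in that light. This stands as far as it goes: s may be 0. The consent script for this chart review is also not among the pages available, so it may have made the window clear. What remains is that the items themselves say otherwise.

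Several stronger readings are tempting and are not supported:

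- *That any routine clinic visit restarts the count in items 8.1–8.3, because the word study is missing there.* This is strained. Item 8.3 counts unplanned clinic visits, and would be close to zero by construction if each one reset its own window.
- *That the OCS result in Table 31b is distorted.* SAP Appendix B does not tie that table to this form. SAP section 3 describes the exacerbation dataset only as EMR or claims data with pre-post information. The ratios of 1.5 to 2.6 also require every analysed form to have been answered literally.
- *That the form leaves no trace of the window used.* The dates in items 8.3 and 8.5 can show it for some patients.
- *That the net bias must be towards a reduction.* A form completed after month 12 could include later events and so lengthen the post window. Only the direction of the literal reading is certain.

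**Conclusion.** The form contradicts itself, and the contradiction appears in every printed copy in the protocol. In a patient with a follow-up study visit at month f, a literal answer gives a spurious fall of f/12 in the expected count, assuming a constant rate. Over the sample it is s × f/12 with s unknown, so the effect on the actual data may be nil or material. The documents do not show which window the sites used. The exploratory methods are redacted, so how they treat these counts cannot be judged.

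The scope is limited: re-consented patients at selected sites, in a comparison outside the stated primary and secondary outcomes of a descriptive study. It is still worth correcting, because the possible error favours the program, there is no control group to expose it, and the remedy is cheap.

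**What to change.** **Form.** Reword items 8.1–8.4 to count events *in the 12 months after the initial study visit*. Pre-print the window start (initial visit date) and end (that date plus 12 months). The cost is four item wordings and two dates.

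**Forms already completed.** SAP Appendix B describes analyses in the past tense, so this is probably the main task.

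1. Ask each selected site which window it used for its re-consented patients.
2. Check the answer against the dates in items 8.3 and 8.5 and against the Follow-up CRF counts. These checks miss many shortened windows, so they do not replace the question.
3. Where a shortened window is confirmed, correct the counts from the chart.
4. Where the completion date on the form is later than initial visit date plus 12 months, have the site remove events after month 12.
5. Repeat the pre/post comparison without forms that are confirmed as shortened but could not be corrected.

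Do not add Follow-up CRF events to the 12-month counts without confirmation; where the lead-in was followed, that would count them twice.

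The cost is one question per selected site, chart re-checks for confirmed cases, and a re-run of the affected tables. No visits or patients are added.
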